##### **5.5.4.3. Prohibited Medications**

The following medications are prohibited during the treatment period of the study:

- Any concurrent anticancer therapy (eg, chemotherapy, radiation therapy, surgery, immunotherapy, biologic therapy) intended to treat malignancy relapse or recurrence. Maintenance therapy with tyrosine kinase inhibitors for high-risk Philadelphia chromosome–positive leukemia and FLT3 inhibitors for FLT3+ acute myeloid leukemia may be used with sponsor approval.
- Any secondary GVHD therapy due to insufficient response/progression on study treatment.
- Concomitant use of targeted therapies with anti-GVHD activity, including but not limited to tumor necrosis factor alpha inhibitors and IL-6 receptor inhibitors.
- Concomitant use of a JAK inhibitor.
- Initiating therapy with an investigational medication unless otherwise approved by the medical monitor.

## **6. STUDY ASSESSMENTS**

All study assessments will be performed as indicated in the schedule of assessments (see [Table 3](#)) and all laboratory assessments will be performed as indicated in [Table 4](#). [Table 5](#) presents a summary of clinical laboratory analytes to be assessed. The order of assessments is suggested by the order of mention within the schedule. See [Section 7](#) for instructions on each assessment. Further details of study procedures and assessments can be found in the study reference manual.

**Table 3: Schedule of Assessments**

Visit Day Item	Section	Screening	Treatment a												EOT d	Re-Treatment d,e	Follow-Up			
		-28 to -1	D1	D7	D14	D21	D28	D35	D42	D49	D56 b	D100	D180	D365 c			Safety f	GVHD g	Survival h	
Informed consent	7.1	X																		
I/E criteria	3	X	X																	
Contact IVRS	7.2	X	X					X				X	X			X	X			
Demography/disease history	7.3	X																		
Prior/concomitant medications	7.4	X	X												X	X	X			
Supportive care medications	5.2.4	X	X												X	X	X			
AE assessment	7.5.1	X	X												X	X	X			
Physical examination	7.5.2	X	X	X	X	X	X	X	X	X	X	X			X	X	X	X		
Vital signs	7.5.3	X	X	X	X	X	X	X	X	X	X	X			X	X	X	X		
ECOG PS	7.5.4	X	X	X	X	X	X	X	X	X	X	X			X	X	X	X		
12-lead ECG	7.5.5	X	As indicated												X					
aGVHD grading and response	6.5.2 7.6.1	X	X	X	X	X	X	X	X	X	X	X	X	X	X	X	X	X g	X	
cGVHD assessment	6.5.2 7.6.2	X	As indicated												X	X	X	X		
Chimerism/graft failure assessment	7.6.3	X	As indicated																	
PTLD assessment	7.6.4		As indicated												X	X	X	X		
Underlying disease relapse assessment	7.6.5		As indicated												X	X	X	X	X	
Dispense study drug	5.1.1		X					X						X		X				
Study drug compliance	5.3		X					X						X	X	X				
Steroid dose monitoring	5.2.2	X	X												X	X				
Survival follow-up	6.5.3																		X	
New aGVHD therapies	6.5.3																		X	

ECG = electrocardiogram; I/E = inclusion/exclusion; PS = performance status; PTLD = post-transplant lymphoproliferative disorder.

**Error! Reference source not found.**a A ± 3-day window is permitted to facilitate scheduling during the treatment phase.

b After Day 56, visits will occur every 28 days and will include all Day 56 assessments.

c The Day 365 visit will also serve as the regularly scheduled visit occurring every 28 days after Day 56 (ie, Day 364).

d A second EOT should occur if the subject restarts itacitinib and subsequently discontinues treatment.

e Re-treatment assessments occur every 28 days ± 3 days.

f 30 to 35 days after EOT.

g Every 28 days ± 7 days, for participants who completed study treatment or discontinued early for reasons other than GVHD progression.

h Every 8 weeks ± 7 days.

**Table 4: Laboratory Assessments**

Visit Day Item	Section	Screening	Treatment a											EOT c	Re-Treatment f	GVHD Follow-Up	Safety Follow-Up g		
		-28 to -1	D1 b	D7	D14	D21	D28	D35	D42	D49	D56 c	D100	D180					D365 d	
Chemistry panel	7.5.6.1	X	X	X	X	X	X	X	X	X	X	X	X	X	X	X	X	X h	X
Hematology	7.5.6.2	X	X	X	X	X	X	X	X	X	X	X	X	X	X	X	X		X
Hepatitis screening	7.5.6.4	X																	
HIV screening	7.5.6.5	X																	
Serum pregnancy test (childbearing females only)	7.5.6.3	X													X				
Urine pregnancy test i (childbearing females only)	7.5.6.3						X				X								
PK assessment j	7.7		X	X			X												

a A ± 3-day window is permitted to facilitate scheduling during the treatment period.  
b Day 1 laboratory assessments do not need to be repeated if screening assessments were performed within the preceding 7 days.  
c After Day 56, visits will occur every 28 days and will include all Day 56 assessments.  
d The Day 365 visit will also serve as the regularly scheduled visit occurring every 28 days after Day 56 (ie, Day 364).  
e A second EOT should occur if the subject restarts itacitinib and subsequently discontinues treatment.  
f Re-treatment assessments occur every 28 days.  
g 30 to 35 days after EOT.  
h Liver testing including total bilirubin data  
i Urine pregnancy tests are required at Day 28 and every 28 days.  
j Subjects 1-112: samples collected on Days 1, 7, and 28 at predose and at 1 hour ± 15 minutes, 2 hours ± 30 minutes, and 5 hours ± 60 minutes postdose. Subjects 113-436: Day 7 and 28 at predose only.  
k Day 56 only.

**Table 5: Clinical Laboratory Analytes**

Serum Chemistries	Hematologya	Other
Albumin	Hematocrit	Serum pregnancy test
ALP	Hemoglobin	Urine pregnancy test
ALT	Mean corpuscular volume	
AST	Reticulocytes	
Bicarbonate or CO 2	Platelet count	
Blood urea nitrogen	Red blood cell count	
Calcium	White blood cell count	
Chloride	White blood cell differential (5 parts):	Hepatitis Screening Tests
Creatinine	• Basophils	Hepatitis B surface antigen
Glucose	• Eosinophils	Hepatitis B surface antibody
Lactate dehydrogenase	• Lymphocytes	Hepatitis B core antibody
Lipid profile (total cholesterol, HDL, LDL, and triglycerides)	• Monocytes	HCV antibody
Phosphorus	• Neutrophils	HCV-RNA
Potassium		HBV-DNA
Sodium		
Total bilirubin		
Total protein		

ALP = alkaline phosphatase; AST = aspartate aminotransferase; HDL=high-density lipoprotein; LDL=low-density lipoprotein.

a Hematology and chemistry assessments will be performed locally.

## 6.1. Screening

The screening period is the interval between signing the ICF and the day the subject is randomized in the study (Day 1). The screening period may not exceed 28 days. Informed consent must be obtained before performing any study-specific procedures that are not considered standard of care. Assessments that are required to demonstrate eligibility may be performed over the course of 1 or more days during this period.

Procedures conducted as part of the subject's routine clinical management (eg, complete blood count) and obtained before signing of informed consent may be used for screening or baseline purposes, provided that the procedure meets the Protocol-defined criteria and has been performed in the timeframe of the study. Results from the screening visit evaluations will be reviewed to confirm subject eligibility before randomization or the administration of study drug. Tests with results that fail eligibility requirements may be repeated once during the screening period if the investigator believes the results to be in error or believes there has been a change in eligibility status (eg, following recovery from an infection). For screening assessments that are repeated, the most recent available result before randomization will be used to determine subject eligibility. Treatment should start as soon as possible but within 2 days after the date of randomization.

## **6.2. Treatment**

The treatment period begins on the day the subject receives the first dose of study drug through the point at which the principal investigator determines the subject will be permanently discontinued from study drug. Dates for subsequent study visits will be determined based upon this day and should occur within  $\pm 3$  days of the scheduled date unless delayed for safety reasons. During the Day 1 visit, results from screening visit evaluations should be reviewed to determine whether the subject continues to meet the eligibility requirements as specified in the Protocol.

## **6.3. End of Treatment**

If a decision is made that the subject will permanently discontinue study treatment, the EOT visit should be conducted. If the EOT visit coincides with a regular study visit, the EOT evaluations will supersede those of that scheduled visit, and the data should be entered in the EOT visit in the eCRF. The subject should be encouraged to return for the follow-up visit.

## **6.4. Re-Treatment**

For subjects who experience aGVHD recurrence after taper of randomized treatment is completed, investigators have the option to use open-label itacitinib plus corticosteroids for the treatment of recurrent aGVHD irrespective of initial randomized treatment. For the purpose of this Protocol, treatment of recurrent aGVHD with open-label itacitinib plus corticosteroids will be called the re-treatment phase. Subjects entering the re-treatment phase will be required to follow the assessment schedule as outlined in [Table 3](#). Corticosteroid tapering will be performed at the investigator's discretion. Investigators wishing to initiate a taper of itacitinib earlier than Day 180 may do so upon consultation with and approval from the sponsor's medical monitor. Subjects may be re-treated with itacitinib only once. Subjects ending the re-treatment phase will repeat the EOT visit and subsequent safety and survival follow-up visits.

## **6.5. Follow-Up**

### **6.5.1. Safety Follow-Up**

The safety follow-up period is the interval between the EOT visit and the scheduled follow-up visit, which should occur 30 to 35 days after the EOT visit (or after the last dose of study drug if the EOT visit was not performed). Adverse events and SAEs must be reported up until at least 30 days after the last dose of study drug, the date of the follow-up visit, or until toxicities resolve, return to baseline, or are deemed irreversible, whichever is longer.

If a subject withdrew from treatment due to reasons other than disease progression, GVHD staging and grading will be repeated at the safety follow-up visit.

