### **7.6. Efficacy Assessments**

#### **7.6.1. GVHD Staging and Grading**

Acute GVHD grading will be performed by the investigator on a weekly basis for the first 8 weeks after randomization, then every 28 days thereafter. GVHD staging and grading will also occur on Days 100, 180, and 365 and at the EOT visit.

On-treatment aGVHD grading should be performed relative to the Day 1 assessment.

If subjects withdrew due to reasons other than GVHD progression, then GVHD staging and grading will be assessed at the safety follow-up visit and every 28 days thereafter during survival follow-up until progression of GVHD, start of new anti-GVHD therapy, or death.

Data regarding the quantification of aGVHD symptoms (extent of skin rash, total bilirubin level, volume of diarrhea) should be reported using MAGIC guidelines ([Harris et al 2016](#)); response will be assessed as per CIBMTR modifications to the IBMTR response index as indicated in [Appendix B \(CIBMTR 2009\)](#).

- Skin:
  - Only areas involved with active erythema should be used for determination of body surface area staging based on the rule of nines.
  - A portion of a body area segment may be used for the quantification.
  - Desquamation or fluid-filled bullae should be reported if present, as these findings are the hallmark of Stage 4 skin GVHD.
- Liver:
  - Liver GVHD staging is based solely on total (not conjugated/direct) serum bilirubin levels.

- Liver GVHD manifesting as transaminitis without concomitant elevation in serum bilirubin should be diagnosed when the presence of GVHD is confirmed by liver biopsy (where appropriate) and score it as Stage 0.
- If bilirubin levels were elevated before the diagnosis of GVHD in another target organ and do not increase further, liver GVHD should not be diagnosed in the absence of biopsy confirmation. However, if hyperbilirubinemia develops at the same time or after the onset of GVHD in another target organ, liver GVHD is presumed to be present in the absence of an identified alternative cause.
- Upper GI:
  - Symptoms of concern for upper GI GVHD include anorexia, nausea, vomiting, and dyspepsia, and assessment depends on close attention to caloric intake and symptom reporting.
  - An upper GI endoscopy should be performed whenever possible to confirm upper GI GVHD; however, the diagnosis may be made without biopsy confirmation.

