### 9.2. Selection of Sample Size

A sample size of 414 subjects with 1:1 randomization (itacitinib vs placebo) and stratification based on aGVHD risk status (standard risk vs high risk) provides approximately 90% power to test for the primary endpoint (ORR at Day 28) and 83% power to test for the key secondary endpoint (NRM at Month 6). The family-wise  $\alpha$ -level will be controlled at 0.025 overall for the two comparisons. Specifically, this study will claim to have achieved the efficacy objective when the primary endpoint ORR at Day 28 shows a significant treatment effect at 1-sided  $\alpha = 0.025$ . Conditional on significance of the primary endpoint, the key secondary endpoint (NRM at Month 6) will be tested at 1-sided  $\alpha = 0.025$ .

An absolute improvement of 16% in the primary endpoint of ORR at Day 28 would be considered a clinically meaningful improvement over standard first-line systemic treatment for aGVHD (standard care ORR at Day 28:  $P_0 = 0.56$ ; itacitinib ORR at Day 28:  $P_1 = 0.72$ ). A sample size of 414 subjects (207 subjects per treatment arm) will provide approximately 90% power to detect a 16% overall difference (72% vs 56%) between treatment cohorts for the primary endpoint (ORR at Day 28) at a 1-sided alpha level of 0.025. A CMH test with 2-strata will be used.

The assumed Day 28 ORR of 56% is based on MacMillan et al (2015). The stratum-specific response rates (standard risk, 68%; high risk, 44%) assume a standard risk:high risk ratio of 0.50:0.50. It is expected that treatment with itacitinib will result in a 16% increase in the ORR, that is, an expected odds ratio of 2.02 (which corresponds to an overall increase in ORR to 72%), with stratum-specific response rates of 81% and 61% for standard-risk and high-risk aGVHD cohorts, respectively. Power for the CMH test with stratification based on GVHD risk score was calculated using software N-Query 5.0.

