### 9.4. Statistical Analyses

#### 9.4.1. Primary Analyses

The primary endpoint is ORR at Day 28, defined as the proportion of subjects demonstrating a CR, VGPR, or PR, as per standard criteria (Harris et al 2016, CIBMTR 2009). The comparison of ORR at Day 28 between treatment cohorts will be conducted once the last subject completes the Day 28 visit or withdraws from the study. A CMH test with normal approximation will be used. Summary statistics and 95% CI will be provided.

Subjects who are missing Day 28 aGVHD response assessment data will be considered to be nonresponders.

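### Subjects who stop study drug on Days 2-24 for reasons other than GVHD progression have no clearly required grading in the Day 28 window, and an ungraded subject counts as a nonresponder on the primary endpoint

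*Protocol*

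**What the plan says.** **Off-treatment grading.** Protocol 6.5.1 covers subjects who leave treatment for reasons other than disease progression: "GVHD staging and grading will be repeated at the safety follow-up visit". Table 3, footnote f, times that visit at "30 to 35 days after EOT". Protocol 7.6.1 repeats the rule for subjects who withdrew for reasons other than GVHD progression: "then GVHD staging and grading will be assessed at the safety follow-up visit and every 28 days thereafter". Protocol 6.5.2 starts its 28-day cycle only after the safety visit. Table 3 places the Day 7 to Day 56 visits under its Treatment heading, and Protocol 6.2 ends the treatment period when study drug is permanently stopped.

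**Text pointing the other way.** Protocol 7.6.1 opens by asking for weekly grading over the eight weeks that follow randomization, and does not restrict this to subjects on drug.

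**Status after stopping.** Protocol 5.5 says that follow-up begins. Protocol 5.5.2 says that the subject is withdrawn from the study.

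**Scoring.** Protocol 9.4.1: "Subjects who are missing Day 28 aGVHD response assessment data will be considered to be nonresponders". SAP 7.3.1.1 lists a missing visit among the nonresponder categories and uses assessments within 3 days of Day 28. SAP 4.1.5 maps an EOT assessment to Day 28 only if it lies within 3 days of the target day. SAP 5.3.3.1 keeps every randomized subject in the denominator.

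**The concern.** Take a subject in complete response who stops on Day 10 for toxicity and stays on corticosteroids without new GVHD therapy. The off-treatment schedule grades this subject at about Day 10 and again on Days 40 to 45. Unless someone arranges an extra assessment, the primary endpoint records a failure because no visit was scheduled.

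This does not look like a declared composite. SAP 7.1 and 7.3.1.1 name new anti-GVHD therapy, death, study withdrawal and a missing visit as routes to nonresponse. Stopping study drug is not named. None of the sensitivity analyses in SAP 7.3.1.2 varies the missing-data rule.

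At stake are power and, if the arms differ in early stopping, the size of the estimated treatment difference.

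**Working it through.** **1. Visit timing.** The window is Day 28 ± 3, that is Days 25-31. With EOT on day e, the off-treatment schedule gives gradings at e, at e+30 to e+35, and every 28 days after that.
- The EOT grading is in the window only if 25 ≤ e ≤ 31.
- The safety visit is in the window only if e+30 ≤ 31, so e = 1.
- Every e from 2 to 24 has no scheduled grading in the window. The earliest safety visit is Day 32 for e = 2, Day 40 for e = 10 and Day 54 for e = 24.

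**2. The plan's own power.** Inputs from Protocol 9.2: 207 per arm; "at a 1-sided alpha level of 0.025"; "The stratum-specific response rates (standard risk, 68%; high risk, 44%) assume a standard risk:high risk ratio of 0.50:0.50"; "with stratum-specific response rates of 81% and 61% for standard-risk and high-risk aGVHD cohorts, respectively". In each stratum, with n per arm, let w = n/2. The stratified CMH power by normal approximation is

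Φ( [Σ w(p_T − p_C) − 1.96·√V0] / √V1 ),

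where V0 = Σ n²·p̄(1−p̄)/(2n−1) and V1 = Σ w²[p_T(1−p_T) + p_C(1−p_C)]/n.

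With n = 103.5 and w = 51.75, the numerator sum is 51.75 × (0.13 + 0.17) = 15.525, √V0 = 4.780 and √V1 = 4.706. Then (15.525 − 9.369)/4.706 = 1.308, and power is 0.905. The stated figure of about 90% is reproduced. The stratum rates average 71% and 56%, a difference of 15.0 points; the text rounds to 72% and 16 points.

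**3. Ungraded subjects scored as nonresponders.** All 436 are kept: 218 per arm, n = 109 per arm per stratum, w = 54.5. Each rate is multiplied by (1 − d), where d is the share of that arm that stops early and is not graded in the window. The overall difference is 0.71(1 − d_T) − 0.56(1 − d_C). **The values of d are assumptions; the documents give none by arm.**

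Example, d_T = 8% and d_C = 3%:
- Rates become 0.7452 vs 0.6596 (standard risk) and 0.5612 vs 0.4268 (high risk).
- The difference is 0.6532 − 0.5432 = 0.110.
- The numerator sum is 54.5 × (0.0856 + 0.1344) = 11.99, √V0 = 5.013 and √V1 = 4.967.
- (11.99 − 9.825)/4.967 = 0.436, so power is 0.67.

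| Itacitinib / placebo ungraded | Difference (points) | Power, single test at 1.96 | Power, boundaries 2.2498 and 2.0155 at t = 0.826 |
|---|---|---|---|
| 0% / 0% | 15.0 | 0.92 | 0.91 |
| 5% / 5% | 14.3 | 0.88 | 0.87 |
| 6% / 3% | 12.4 | 0.78 | 0.77 |
| 8% / 3% | 11.0 | 0.67 | 0.66 |

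**4. Direction when there is no true effect.** Placebo rates are used in both arms, with a single 1-sided test.
- Equal 5%: type I error 0.025.
- Itacitinib 10%, placebo 5%: 0.005.
- Itacitinib 5%, placebo 10%: 0.086.

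**5. How much depends on the stoppers' true response.** Suppose that stoppers would respond at half the planned rate and all are graded. At 8% vs 3% the difference is 0.71 × 0.96 − 0.56 × 0.985 = 0.130, and power with the boundaries is about 0.81. Of the total fall from 0.91 to 0.66 (about 0.25), about 0.15 then comes from the missing grading.

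**6. The sample-size allowance.** 414/0.95 = 435.8, rounded up to 436. This restores power only if early losses leave the analysis. Under the full analysis set they stay in as nonresponders, so at 5% per arm power is about 0.88.

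**The case against.** A reader might infer that these subjects are never graded on Days 25-31. The documents do not say that. The opening sentence of Protocol 7.6.1 can be read as covering everyone for eight weeks, with the later paragraph adding visits. Protocol 6.6 allows unscheduled visits at any time, and SAP 4.1.5, 7.2 and 7.3.1.1 accept an unscheduled assessment in the window. This stands, and it limits the claim to grading that is not clearly required. It does not close the gap. Table 3 and the specific rule in 7.6.1 would lead a site to skip Day 28, and discretionary visits make ascertainment depend on the site.

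A reader might also infer that poor tolerability of itacitinib biases the endpoint as a matter of course. That does not follow either. No stopping rates by arm are given. For low neutrophils or platelets, Table 1 mostly provides for dose reduction or temporary interruption, and those subjects remain in the treatment period with their Day 28 visit. Early stops remain possible, since Table 1 requires discontinuation for other Grade 4 toxicity. If itacitinib did have more of them, the error would run against itacitinib; a raised false-positive rate needs more such stopping on placebo.

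Finally, subjects who die, leave the study or start new GVHD therapy before Day 28 are nonresponders under SAP 7.3.1.1 in any case, so only the remainder are affected. This stands too.

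**Conclusion.** The concern holds as a scheduling gap with a conditional effect on the primary endpoint. For an EOT on Days 2-24 for reasons other than GVHD progression, the off-treatment schedule places no grading on Days 25-31. Protocol 7.6.1 is internally inconsistent on whether weekly grading continues, and an ungraded responder is scored a failure.

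Equal stopping in both arms mainly dilutes the effect: at an assumed 5% per arm, power is 0.87-0.88. Unequal stopping shifts the estimate toward the arm with fewer stops. The 8% vs 3% case (11.0 points, power 0.66-0.67) is an upper bound for that split: it assumes that stoppers would respond at the planned rate and that none is graded in the window. The documents support neither a definite bias nor a definite direction.

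**What to change.** 1. State in Protocol 6.5 and 7.6.1, and mark in Table 3, that aGVHD grading at Day 28 (± 3 days) is done for every randomized subject who has not died or withdrawn consent for follow-up, whether or not study drug has stopped. Use that grading in the primary analysis, subject to the existing new-therapy rule.
2. Reconcile Protocol 5.5.2 (withdrawn from the study) with 5.5 (follow-up begins); otherwise the affected subjects could fall outside item 1. Reconcile the two grading rules within 7.6.1.
3. Add to SAP 7.3.1.2 a sensitivity analysis for missing Day 28 response, such as multiple imputation or a tipping-point analysis, and report by arm how many subjects are ungraded after stopping drug early. Item 1 cannot recover subjects already past Day 28. The Interim 2 cutoff was 17 APR 2019, and SAP Appendix D tabulates boundaries for 410 to 435 of 436 subjects, so for most of the trial this item is the one that helps.

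Cost: a protocol clarification, one routine clinical grading for a few subjects, and a little extra analysis.

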### **6.5.2. Post-Treatment GVHD Follow-Up**

Subjects who completed study treatment or discontinued treatment for reasons other than GVHD progression will be followed every 28 days ( $\pm 7$  days) after the safety follow-up visit until any of the following occurs:

- GVHD progression.
- Initiation of a new anti-GVHD therapy.
- Relapse/recurrence of underlying hematologic disease.
- A maximum of 12 months from EOT or a maximum of 24 months from Day 1 is reached, whichever occurs first.

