Evaluate the use and discontinuation of corticosteroids.	Average and cumulative corticosteroid dose at Days 28, 56, 100, and 180; proportion of subjects who discontinue corticosteroids at Days 56 and 100.
Evaluate the use and discontinuation of immunosuppressive medications.	Proportion of subjects who discontinue immunosuppressive medications at Days 56 and 100.
Evaluate the incidence of aGVHD flares.	Incidence rate of aGVHD flares through Day 100.
Evaluate the incidence of cGVHD.	Incidence rate of cGVHD at Days 180 and 365.

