### **6.5.3. Survival Follow-Up**

Subjects who complete post-treatment follow-up or experience GVHD progression or require a new anti-GVHD therapy should be contacted by telephone, email, or visit at least every 8 weeks ( $\pm 7$  days) to assess for new GVHD therapy and survival status until death, withdrawal of consent, or the end of the study, whichever occurs first.

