### **7.6.2. Chronic GVHD Assessment**

Subjects will be assessed for signs and symptoms of cGVHD according to local institutional practice at screening, during the treatment phase, at the end of treatment, and during re-treatment (if applicable) as indicated in [Table 3](#). Definitive and possible manifestations of cGVHD should be assessed as per NIH consensus guidelines for cGVHD ([Jagasia et al 2015](#)).

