7.5. Other Secondary Efficacy Analyses

Secondary graft failure will be tabulated with summary statistics.

Incidence rate of aGVHD flares through Day 100 will be summarized. Summary statistics will be provided.

Average and cumulative corticosteroid dose during the weeks ending on Days 28, 56, 100, and 180 will be tabulated. Proportions of subjects who discontinue corticosteroids will be summarized.

Proportions of subjects who discontinue immunosuppressive medication on Days 56 and 100 will be tabulated. Summary statistics will be provided.

Incidence of cGVHD (Days 180 and 365 and overall) will be estimated. Summary statistics will be provided.

[REDACTED]

Subgroup analyses will be conducted by underlying hematologic disease (malignant vs nonmalignant), as appropriate.

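### After the safety follow-up visit no cGVHD assessment is scheduled for subjects who progress, start new anti-GVHD therapy or relapse, so Day 180 and Day 365 cGVHD incidence has outcome-dependent missing data

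*Protocol*

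**What the plan says.** Protocol Section 2 gives the endpoint as "Incidence rate of cGVHD at Days 180 and 365". SAP 7.5 repeats it: "Incidence of cGVHD (Days 180 and 365 and overall) will be estimated", with summary statistics. SAP 5.3.3 presents efficacy analyses by planned treatment group, and SAP 5.3.3.1 uses all randomised subjects for efficacy data. No denominator, censoring rule or treatment of death is given for cGVHD. SAP 4.1.8 says that missing values are not imputed unless a method is stated, and none is stated here.

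On observation after treatment:

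- Protocol 6.5.2 opens GVHD follow-up to a limited group: "Subjects who completed study treatment or discontinued treatment for reasons other than GVHD progression will be followed every 28 days". Footnote g of Table 3 has the same limit: "for participants who completed study treatment or discontinued early for reasons other than GVHD progression".
- Follow-up under 6.5.2 ends at GVHD progression, at relapse of the underlying disease, at a time cap, or at "Initiation of a new anti-GVHD therapy".
- From then on, 6.5.3 provides a contact at least every 8 weeks "to assess for new GVHD therapy and survival status until death", withdrawal of consent or study end.
- In Table 3 the cGVHD row is marked at screening, as indicated on treatment, and at end of treatment (EOT), re-treatment, safety follow-up and GVHD follow-up. It has no mark under survival follow-up. SAP Table 3 agrees.
- Protocol 7.6.2 lists screening, treatment, EOT and re-treatment, and names no follow-up visit.
- Protocol 5.5.1 requires withdrawal from study treatment when additional systemic therapy is needed for GVHD progression or lack of response.

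**The concern.** Failure of acute GVHD treatment leads, through 5.5.1 and 6.5.2, out of every visit at which cGVHD is scheduled to be assessed. A subject who fails early can reach Day 180 and Day 365 alive and in contact with the site, yet have no recorded cGVHD status at either time. The trial expects treatment to change how often this happens, so the loss is not random with respect to arm.

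What is at stake is how two percentages will be read in the study report. If unobserved subjects are counted as free of cGVHD, the arm with more failures looks better than it is, and a drug that prevents failure can appear to cause cGVHD. If only observed subjects are counted, each arm's figure describes a group selected by treatment success.

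**Working it through.** **Plan's own figure.** The documents give none for cGVHD. The proxy for failure comes from the Day 28 ORR assumptions in Protocol 9.2, so I checked those first. With 207 per arm, two equal strata (m = 103.5 per arm per stratum, 207 subjects in all) and rates of 68% vs 81% and 44% vs 61%, the CMH normal approximation without continuity correction has:

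- weighted difference = 51.75 × (0.13 + 0.17) = 15.525
- null SD = √[103.5² × (0.745 × 0.255 + 0.525 × 0.475) / 206] = 4.780
- alternative SD = √[25.875 × (0.3715 + 0.4843)] = 4.706
- power = Φ[(15.525 − 1.96 × 4.780) / 4.706] = Φ(1.308) = 0.905

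This agrees with the stated 90%.

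**Last scheduled cGVHD check.** For EOT at Day 28 after progression, the safety visit falls at Day 28 + 30 to 35 = Day 58 to 63, and nothing follows. The safety visit reaches Day 180 only if EOT is at about Day 145 to 150 or later, and Day 365 only if EOT is at about Day 330 to 335 or later.

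**Share of the loss by arm.** Planned nonresponse is 1 − 0.56 = 0.44 on placebo and 1 − 0.72 = 0.28 on itacitinib. Let k be the assumed share of nonresponders who leave cGVHD follow-up.

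- k = 1: 218 × 0.44 = 95.9 vs 218 × 0.28 = 61.0
- k = 0.5: 48.0 vs 30.5
- Placebo share for any common k: 0.44 / (0.44 + 0.28) = 61%

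**All randomised subjects as denominator, unobserved counted as no cGVHD.** With an assumed true incidence c, equal in both arms and in failures, observed incidence = c × (1 − k × nonresponse).

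| c | k | Placebo | Itacitinib | False excess (points) |
|---|---|---|---|---|
| 20% | 1 | 11.2% | 14.4% | 3.2 |
| 30% | 1 | 16.8% | 21.6% | 4.8 |
| 40% | 1 | 22.4% | 28.8% | 6.4 |
| 20% | 0.5 | 15.6% | 17.2% | 1.6 |
| 30% | 0.5 | 23.4% | 25.8% | 2.4 |
| 40% | 0.5 | 31.2% | 34.4% | 3.2 |

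**Allowing for deaths (c = 30%, k = 1).** Take the planned Month 6 nonrelapse mortality of 33% vs 19.8% and assume that subjects who die by then contribute no cGVHD. Only living nonresponders are then lost because of the follow-up rule.

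- Deaths independent of response: 0.44 × 0.67 = 29.5% vs 0.28 × 0.802 = 22.5%. Part of the gap due to the rule: 0.30 × (0.295 − 0.225) = 2.1 points.
- All these deaths among nonresponders: 0.44 − 0.33 = 11.0% vs 0.28 − 0.198 = 8.2%. Part due to the rule: 0.30 × 0.028 = 0.8 points.

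**Assessed subjects only as denominator (k = 1, deaths ignored).** Let failures carry r times the cGVHD risk c of non-failures. The true difference, placebo minus itacitinib, is c × (r − 1) × (0.44 − 0.28), while the observed difference is 0.

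- r = 1: no bias
- r = 1.5, c = 20%: 0.20 × 0.5 × 0.16 = 1.6 points hidden
- r = 2, c = 30%: 0.30 × 1 × 0.16 = 4.8 points hidden

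**The case against.** The other side has several sound points.

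- A reader might infer that cGVHD assessment stops as soon as a subject leaves treatment. It does not. Table 3 marks it at EOT and at the safety visit, with no exclusion for progression, so failures shortly before Day 180 or Day 365 can still be captured.
- The objective is to evaluate cGVHD incidence, whereas the Protocol uses the verb compare for response and longer-term outcomes. No between-arm test is planned.
- The larger figures need a counting rule that neither document states. With equal risk in failures and non-failures, an assessed-only denominator is unbiased.
- Nonresponse overstates the loss. SAP 7.3.1.1 counts death, study withdrawal and missed visits as nonresponse. A missed visit does not end cGVHD follow-up, and a death is not a loss caused by 6.5.2.
- Failure-free survival is largely protected, because new anti-GVHD therapy is itself an event (SAP 7.4.9).
- The SAP could instead define the estimate as cGVHD before progression or new therapy. That is a legitimate quantity.

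These points reduce the size and importance of the problem without removing it. The results will still be shown by arm, and the status of early failures will still be unknown. Redefining the quantity would answer a different question from incidence at Days 180 and 365, and SAP wording cannot recover data that were not collected. Other routes are unreliable: Protocol 8.1.2 requires monitoring for new adverse events only for at least 30 days after the last dose, and the therapy row in Table 3's survival column is for acute GVHD.

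**Conclusion.** The point holds as a gap in data collection for a descriptive secondary endpoint. After the safety visit, Day 180 and Day 365 cGVHD status is not scheduled to be observed for most early treatment failures, and the loss depends on an outcome that the trial expects to differ between arms.

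If unobserved subjects are counted as cGVHD-free, the false excess on itacitinib is 3.2 to 6.4 points when every Day 28 nonresponder is lost and 1.6 to 3.2 points when half are, over an assumed true incidence of 20% to 40%. At 30% incidence, allowing for deaths brings it to about 0.8 to 2.1 points. Failures after Day 28 would add to these figures, but the documents give no rate for them. With assessed subjects only, bias arises only if cGVHD risk differs between failures and non-failures.

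A reader might go further and infer that the missing data lie overwhelmingly on placebo, or that no fair reading of cGVHD by arm is possible. The documents do not support either. They give no treatment-failure rates, the ORR proxy gives about 61% vs 39%, and the bias depends on an unstated denominator and an unknown risk among failures. The primary and key secondary endpoints are unaffected. This is a cheap improvement, not a flaw in the main comparison.

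**What to change.** - **Protocol 6.5.3 and Table 3:** add one item to the existing 8-weekly survival contact, asking whether cGVHD has been diagnosed since the last contact and, if so, its onset date. Collect it for all subjects through at least Day 365, whatever the reason for stopping treatment. Table 3 already records relapse and new therapies at this contact.
- **SAP 7.5:** estimate cGVHD incidence at Days 180 and 365 by arm in all randomised subjects, as a cumulative incidence with death without cGVHD as a competing event and censoring at the last known cGVHD status. The rule for death is needed because planned mortality differs by arm.
- **Protocol 7.6.2:** reconcile its list of assessment times with Table 3, which also marks safety and GVHD follow-up.

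The cost is one question, one eCRF field and a short SAP paragraph. Sample size, power and alpha do not change. On the proxy, the loss caused by the rule falls from 96 vs 61 subjects (all nonresponders lost) or 48 vs 31 (half lost) to about zero in each arm. Death, withdrawal of consent and loss to follow-up remain. The downside is that cGVHD status taken by telephone, email or visit is less precise than a scheduled examination.
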